6.4.1 Retesting During Screening or Lead-in Period

Participant Re-enrollment: This study permits the re-enrollment of a participant who has discontinued the study as a pretreatment failure (ie, participant has not been randomized/has not been treated). If re-enrolled, the participant must be re-consented. If the initial screen failure was due to a medical concern (eg, TB assessment), the site must notify the Clinical Trial Physician/Medical Monitor of the intent to rescreen, describe the cause of the initial screen failure and the resolution of the medical consent, and receive approval prior to proceeding. This communication must be documented in the study record.

All screening procedures are to be performed within 4 weeks of the randomization visit except as described below.

6.4.1.1 Retesting

Retesting of laboratory parameters and/or other assessments within any single Screening or Lead-in period will be permitted (in addition to any parameters that require a confirmatory value) for laboratory errors.

The most current result prior to Randomization is the value by which study inclusion will be assessed, as it represents the participant's most current, clinical state.

Laboratory parameters and/or assessments that are included in [Table 2-1](#) may be repeated in an effort to find all possible well-qualified participants. Consultation with the Clinical Trial Physician/Medical Monitor may be needed to identify whether repeat testing of any particular parameter is clinically relevant.

6.4.1.2 Extended Screening

Participants who experience a delay in completing screening may extend the screening period to 42 days, as long as this delay was not due to an intercurrent significant medical illness such as an infection requiring hospitalization or administration of parenteral antibiotic agents. This extension is intended to address nonmedical issues or extended medical assessments (eg, acute infection or assessment of latent TB). For medical events, like initiation of treatment for latent TB, consideration should be given to screen failure with the expectation of rescreening after resolution and approval from the Clinical Trial Physician/Medical Monitor.

If screening is extended beyond 28 days, all screening procedures except IRT enrollment, height/weight, urinalysis, anti-CCP-2, RF, HLA-DRB1 SE alleles, chest x-ray, TB, hepatitis B

virus (HBV)/hepatitis C virus (HCV), and HIV testing, should be repeated prior to randomization, as noted in [Table 2-1](#).

6.4.1.3 Rescreening

This study permits the rescreening of a participant who has discontinued the study as a pretreatment failure (ie, participant has not been randomized/has not been treated) and still meets all inclusion/exclusion criteria. If rescreened, the participant must be re-consented. A participant may be rescreened only once. Clinical Trial Physician/Medical Monitor approval is required for screen failures due to medical concerns, and rescreens are not permitted less than 28 days after signing the first ICF. The participant will need to sign a new ICF and be re-enrolled with a new participant number via the IRT. Chest x-ray and TB screening will not be repeated if they were performed within the last 3 months, and prior results must be added to the study record. SE genotyping will not be repeated, and results from prior testing should be added to the study record.

7 TREATMENT

Study treatment is defined as any investigational treatment(s), marketed product(s), placebo, or medical device intended to be administered to a study participant according to the study randomization or treatment allocation.

Study treatment includes both IP/investigational medicinal product (IMP) and non-IP/non-IMP, and can consist of the following (see [Table 7-1](#)):

IPs to be supplied by the Sponsor:

- Abatacept (BMS-188667)
- Adalimumab (citrate-free formulation in prefilled syringe)

Non-IPs (the Sponsor will not provide non-IPs):

- MTX
- Corticosteroids
- NSAIDs (including aspirin)
- Folic acid and/or folinic acid (leucovorin)

An IP, also known as IMP in some regions, is defined as a pharmaceutical form of an active substance or placebo being tested or used as a reference in a clinical study, including products already with a marketing authorization but used or assembled (formulated or packaged) differently than the authorized form, or used for an unauthorized indication, or when used to gain further information about the authorized form.

Other medications used as support or escape medication for preventative, diagnostic, or therapeutic reasons, as components of the standard of care for a given diagnosis, may be considered as non-IP.

Table 7-1: Study Treatments for IM101863

Product Description/ Class and Dosage Form	Potency	IP/ Non-IMP	Blinded or Open-label	Packaging/ Appearance	Storage Conditions (per label)
Abatacept Injection	125 mg/mL	IP	Open-label	Prefilled syringe	Refer to the label on the container.
Adalimumab Injection	40 mg/0.4 mL	IP	Open-label	Prefilled syringe	Refer to the label on the container.

Abbreviations: IMP, investigational medicinal product; IP, investigational product.

7.1 Treatments Administered

The selection and timing of dose for each participant is provided in Table 7.1-1.

Table 7.1-1: Selection and Timing of Dose

Study Treatment	Unit Dose Strength(s)/ Dosage Level(s)	Dosage Formulation Frequency of Administration	Route of Administration
Abatacept	125 mg	Weekly	SC injection
Adalimumab	40 mg	Once every 2 weeks	SC injection

Abbreviations: mg, milligram; SC, subcutaneous.

On “office visit” days, study medication should be administered AFTER all assessments have been completed.

7.1.1 Abatacept Treatment

On Day 1, participants will self-administer abatacept 125 mg SC from a prefilled syringe. On Day 8, participants will self-administer abatacept 125 mg SC. Thereafter, participants will self-administer abatacept 125 mg SC once every 7 days, up to and including Week 103 (Day 722).

Participants randomized to adalimumab will switch to abatacept 125 mg SC weekly at Week 24 (Day 169).

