	Day 169	Day 197	Day 225	Day 253	Day 281	Day 309	Day 337	Day 365	Day 421	Day 477	Day 533	Day 589	Day 645	Day 729	
Physician Global Assessment of Disease Activity		X	X	X	X	X	X	X	X	X	X	X	X	X	Must be performed by a blinded Clinical Assessor (see Section 9.1.1 and to Appendix 7).
Physical Function (HAQ-DI)		X	X	X	X	X	X	X	X	X	X	X	X	X	See Appendix 8 .
Quality of Life Scale (SF-36)								X						X	See Appendix 9 .
Work Productivity and Activity (WPAI-RA v2)								X						X	See Appendix 10 .
Fatigue (FACIT-F v4)								X						X	See Appendix 11 .
Duration of Morning Stiffness								X						X	See Appendix 12 .
Study Treatment Administration															
Contact IRT	X	X	X	X	X	X	X	X	X	X	X	X	X	X	Contact of IRT is required to dispense medication at each office visit.
Dispense Diary Cards	X	X	X	X	X	X	X	X	X	X	X	X	X	X	
Collect and Review Diary Cards		X	X	X	X	X	X	X	X	X	X	X	X	X	

Table 2-3: On-treatment Procedural Outline (IM101863): Open-label Treatment Period (OLTP)

Procedure	Wk 24b V7b (± 3 Days)	Wk 28 V8 (± 7 Days)	Wk 32 V9 (± 7 Days)	Wk 36 V10 (± 7 Days)	Wk 40 V11 (± 7 Days)	Wk 44 V12 (± 7 Days)	Wk 48 V13 (± 7 Days)	Wk 52 V14 (± 7 Days)	Wk 60 V15 (± 7 Days)	Wk 68 V16 (± 7 Days)	Wk 76 V17 (± 7 Days)	Wk 84 V18 (± 7 Days)	Wk 92 V19 (± 7 Days)	Wk 104/ET V20 (± 7 Days)	Notes
	Day 169	Day 197	Day 225	Day 253	Day 281	Day 309	Day 337	Day 365	Day 421	Day 477	Day 533	Day 589	Day 645	Day 729	
Dispense Urine Pregnancy Kits for WOCBP for Home Use Every 4 Weeks									X	X	X	X	X	X	Not applicable if serum pregnancy testing is required per local regulations.
Dosing of Weekly Abatacept	X	X	X	X	X	X	X	X	X	X	X	X	X	X	Abatacept must be self-administered weekly between visits. See Section 7.1 .
Dispense Abatacept Kits	X	X	X	X	X	X	X	X	X	X	X	X	X	X	See Section 7.2 .
Reconciliation of Abatacept Kits		X	X	X	X	X	X	X	X	X	X	X	X	X	

Abbreviations: anti-CCP-2, anti-cyclic citrullinated peptide-2; CBC, complete blood count; ET, early termination; FACIT-F, Functional Assessment of Chronic Illness Therapy - Fatigue; HAQ-DI, Health Assessment Questionnaire Disability Index; hsCRP, high-sensitivity C-reactive protein; IRT, Interactive Response Technology; [REDACTED] RF, rheumatoid factor; [REDACTED] SF-36, 36-item Short Form Survey; V, Visit; Wk, Week; WOCBP, women of childbearing potential; WPAI-RA, Work Productivity and Activity Impairment Questionnaire - Rheumatoid Arthritis.

Table 2-4: Post-treatment Follow-up Period (PTFUP; IM101863)

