7.1.2 Adalimumab Treatment

Participants randomized to adalimumab will self-administer an initial dose of adalimumab 40 mg SC from a prefilled syringe on Day 1. On Day 15, participants will self-administer adalimumab 40 mg SC. Thereafter, participants will self-administer adalimumab 40 mg SC once every 14 days, up to and including Week 22 (Day 155).

Participants randomized to adalimumab will switch to abatacept 125 mg SC weekly at Week 24 and continue with the self-administration of abatacept 125 mg SC once every 7 days, up to and including Week 103.

Participants not wishing to continue on open-label abatacept have the option of discontinuing treatment at the end of the SBTP and proceeding to the PTFUP.

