7.2 Method of Treatment Assignment

All participants will be centrally randomized using an IRT. Before the study is initiated, each user will receive log-in information and directions on how to access the IRT. Each participant will be assigned a unique participant number after signing the ICF. Participant numbers will be used on all participants' study information. Participant numbers will not be reassigned. The investigator or designee will register the participant for enrollment by following the enrollment procedures established by the Sponsor.

The following information is required for enrollment:

- Date that informed consent was obtained
- Year of birth
- Gender at birth

Once enrolled in IRT, enrolled participants who have met all eligibility criteria will be ready to be randomized through the IRT. The following information is required for participant randomization:

- Participant number
- Year of birth
- Gender at birth (female or male)
- SE status (positive or negative)

The exact procedures for using the IRT will be detailed in the IRT manual.

Study treatment will be dispensed at the study visits as listed in [Section 2](#) (Schedule of Activities). Sufficient drug will be dispensed at each visit to cover treatment until the next scheduled visit. These will be in intervals of 4, 8, or 12 weeks according to the visit schedule.

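### Table 2-3 ticks abatacept dosing and kit dispensing at Week 104/ET, but Sections 7.1.1 and 7.1.2 end abatacept at Week 103; separately, its home pregnancy-kit row is blank at Week 52

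*Combined protocol and SAP*

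**What the plan says.** **Text.** Section 7.1.1: "Thereafter, participants will self-administer abatacept 125 mg SC once every 7 days, up to and including Week 103 (Day 722"). Section 7.1.2 says that participants switched at Week 24 "continue with the self-administration of abatacept 125 mg SC once every 7 days, up to and including Week 103". Section 7.2 ties supply to the visit calendar: "Sufficient drug will be dispensed at each visit to cover treatment until the next scheduled visit", and "These will be in intervals of 4, 8, or 12 weeks according to the visit schedule". Section 9.4 places the early-termination visit as soon as possible after the last dose. Section 5.1.3 starts follow-up on Day 729 for completers.

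**Table 2-3.** There are 14 visit columns, from Week 24b to Week 104/ET (Day 729). Four rows carry 14 ticks each: IRT contact, diary-card dispensing, weekly abatacept dosing and abatacept kit dispensing. The dosing Note reads "Abatacept must be self-administered weekly between visits" and refers to Section 7.1. The kit Note refers to Section 7.2. The IRT Note reads "Contact of IRT is required to dispense medication at each office visit".

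**Pregnancy kits.** The row "Dispense Urine Pregnancy Kits for WOCBP for Home Use Every 4 Weeks" is blank from Week 24b to Week 52 and ticked at Weeks 60, 68, 76, 84, 92 and 104/ET. Its Note excludes places where local regulations require serum testing.

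**The concern.** The text and the table give different last visits for giving and supplying abatacept, and the documents do not say which prevails. The references also run in a circle. The Table 2-3 Notes send the reader to Sections 7.1 and 7.2, while Section 7.2 sends the reader back to the schedule: "Study treatment will be dispensed at the study visits as listed in" Section 2. The table is therefore an operative instruction to sites.

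What is at stake is one weekly injection, one dispensing step and the diary cards that go with it, all at the point where treatment ends. The last-dose date also anchors the 56-day safety window in Section 10.3.2. Counted from the two nominal dates, that window ends on Day 722 + 56 = 778 or Day 729 + 56 = 785.

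The same column serves early termination, where a dosing tick sits badly with Section 9.4.

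The pregnancy-kit row raises a separate question. Section 6.1 sends readers to Section 2 for on-study pregnancy testing, so a blank cell in that row means a test that is not supplied.

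**Working it through.** **Calendar check.** Day = 7 × week + 1. Week 103 gives 7 × 103 + 1 = 722, which reproduces the day in Section 7.1.1. Week 104 gives 7 × 104 + 1 = 729, which reproduces the table header. The two places therefore use the same calendar, and the difference is not a labelling convention.

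**Cell count.** Fourteen ticks fill fourteen columns in the dosing, kit and diary rows. The Week 104/ET tick in those rows therefore does not depend on how the table was extracted.

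**Nominal weekly doses.**

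- Abatacept throughout, by the text: (722 − 1)/7 + 1 = 104. With the Day 729 tick: (729 − 1)/7 + 1 = 105.
- Switched from adalimumab, by the text: (722 − 169)/7 + 1 = 80. With the Day 729 tick: (729 − 169)/7 + 1 = 81.

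**Supply under Section 7.2** (each visit covers the time to the next scheduled visit).

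- Weeks 24b, 28, 32, 36, 40, 44, 48: 7 visits × 4 weeks = 28 doses.
- Weeks 52, 60, 68, 76, 84: 5 visits × 8 weeks = 40 doses.
- Week 92: 1 visit × 12 weeks = 12 doses, which matches (722 − 645)/7 + 1 = 12 from Day 645 to Day 722.
- Total: 13 visits and 28 + 40 + 12 = 80 doses.

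This is exactly the count from Day 169 to Day 722. For the arm on abatacept throughout, the single-blind period adds 6 visits × 4 = 24, and 24 + 80 = 104. The fourteenth dispensing tick has no later treatment visit to cover. Diary cards ticked for dispensing at that visit have no later collection visit in Table 2-3 or Table 2-4.

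**Pregnancy kits.** The visit gaps longer than 4 weeks are Weeks 52–60, 60–68, 68–76, 76–84, 84–92 and 92–104, six in all. The four-weekly points that fall between visits are Weeks 56, 64, 72, 80, 88, 96 and 100, seven in all. If a kit covers the gap that follows the visit where it is handed out, the ticks at Weeks 60, 68, 76, 84 and 92 cover five gaps and six points. The uncovered gap is Weeks 52–60, and the uncovered point is Week 56 (Day 7 × 56 + 1 = 393). Office urine tests are ticked at Weeks 52 and 60.

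**The case against.** The strongest reply is that the text provisions agree and a careful site would follow them. The last dose is explicit in Section 7.1.1. Section 7.2 dispenses only up to a next visit. Section 7.8 ends sponsor supply with the open-label period unless the study is extended. Follow-up for completers begins on Day 729. The two rows in question point to Sections 7.1 and 7.2. This makes an actual dosing error unlikely, and that part of the reply stands. It does not remove the tick or supply a rule of precedence.

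A reader might infer more than the documents support in four ways:

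- **That the table orders re-dosing of early-termination participants.** This follows only from a literal reading of a shared column header. Those participants have stopped treatment, and Section 9.4 puts their visit after the last dose. Table 2-2 leaves its own Week 24a/ET column blank for dosing and dispensing, which shows that the two tables are laid out differently, not that re-dosing is intended.
- **That the IRT tick is itself an error.** The IRT Note makes contact a condition of dispensing and does not order dispensing at every visit. Table 2-2 carries the same Note with a blank Week 24a/ET cell. IRT contact at Week 104 contradicts nothing.
- **That the Week 104/ET pregnancy-kit tick is wrong.** It can serve the follow-up urine tests in Table 2-4, where a telephone visit may confirm the result.
- **That Section 9 ranks the schedule above the text.** It calls adherence to the study design requirements essential, and Section 2 is named as included among them. Section 7 is covered equally.

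The totals of 105 and 81 are arithmetic from the tick. The protocol states neither.

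**Conclusion.** The inconsistency holds for the dosing and abatacept-kit ticks at Week 104/ET, and for the diary-card tick that goes with them. Its size is one nominal dose and one dispensing step beyond the text. This rests on nominal study days and on the Section 7.2 supply rule as written, and confidence is high because the cell count does not depend on alignment. The supply arithmetic shows that Sections 7.1.1, 7.1.2 and 7.2 agree with one another. It does not settle which end point the sponsor intends, and no view is offered on that.

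The blank Week 52 pregnancy-kit cell is a separate and less certain finding. It affects 1 of 6 long visit gaps and 1 of 7 between-visit points, only where home urine testing applies, with office tests on either side. It depends on extracted blank cells. The row has its full number of cells, but the positions should be checked against the source PDF.

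Severity is minor. No alpha, power, sample size or Week 24 analysis is affected.

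**What to change.** Reconcile the Week 104/ET ticks for abatacept dosing, abatacept kit dispensing and diary-card dispensing in Table 2-3 with Sections 7.1.1, 7.1.2, 7.2 and 9.4. Reconcile the blank Week 52 cell in the home pregnancy-kit row with that row's four-weekly label, after checking the cell positions in the source PDF. In both cases the sponsor should state which schedule is intended. The IRT-contact tick and the Week 104/ET pregnancy-kit tick need no change on their own. The cost is a table correction in the next amendment, with no effect on the design or the analyses.

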7.1.1.1 Abatacept Self-administration of Subcutaneous Injection

Each prefilled syringe contains 1 weekly dose of abatacept, 125 mg/mL. Participants will be trained to self-administer their weekly SC injection. Training should be performed by investigational personnel who are considered qualified trainers by the site principal investigator. A procedure guide will be provided by the Sponsor. The participant should be able to self-administer the SC injection between office visits or have an office-trained caregiver do so.

On office visit days, SC injections should be given AFTER all assessments are completed, including blood draws. If a caregiver is responsible for giving the injections, he or she should accompany the participant to office visits.

7.1.1.2 Abatacept Administration Window

SC injections of study medication may be administered ± 3 days around the target day. The last dose before each office visit should be administered at least 4 days before the scheduled visit date. If an SC injection is not given within the administration window, the next SC injection should be given on the next scheduled target administration day.

7.1.2 Adalimumab Treatment

Participants randomized to adalimumab will self-administer an initial dose of adalimumab 40 mg SC from a prefilled syringe on Day 1. On Day 15, participants will self-administer adalimumab 40 mg SC. Thereafter, participants will self-administer adalimumab 40 mg SC once every 14 days, up to and including Week 22 (Day 155).

Participants randomized to adalimumab will switch to abatacept 125 mg SC weekly at Week 24 and continue with the self-administration of abatacept 125 mg SC once every 7 days, up to and including Week 103.

Participants not wishing to continue on open-label abatacept have the option of discontinuing treatment at the end of the SBTP and proceeding to the PTFUP.

7.1.2.1 Adalimumab Self-administration of Subcutaneous Injection

Each prefilled syringe contains 1 biweekly dose of adalimumab, 40 mg/0.4 mL. Participants will be trained to self-administer their biweekly SC injection. Training should be performed by investigational personnel who are considered qualified trainers by the site principal investigator. A procedure guide will be provided by the Sponsor. The participant should be able to self-administer the SC injection between office visits or have an office-trained caregiver do so.

On office visit days, SC injections should be given AFTER all assessments are completed, including blood draws. If a caregiver is responsible for giving the injections, he or she should accompany the participant to office visits.

7.1.2.2 Adalimumab Administration Window

SC injections of study medication may be administered ± 7 days around the target day. The last dose before each office visit should be administered at least 7 days before the scheduled visit date. If an SC injection is not given within the administration window, the next SC injection should be given on the next scheduled target administration day.

7.1.3 Guidelines for Methotrexate

Participants must enroll on a stable dose of maximum tolerated oral or parenteral MTX (minimum of 15 mg and maximum of 25 mg per week) for at least 4 weeks prior to randomization.

Participants may enroll with MTX doses < 15 mg/week but ≥ 7.5 mg/week if intolerance to higher doses has been recorded in the source documents and the dose of oral or parenteral MTX is stable for 4 weeks prior to randomization. Participants in Japan may also enroll at doses between 7.5 and 15 mg per week at the discretion of the investigator.

All participants must be maintained on the enrollment MTX dose during the SBTP, unless toxicity or intolerability occurs during the course of the study. In that event, the dose may be reduced or held as medically necessary for AEs. However, MTX should be returned to the baseline dose as soon as possible, or to the maximally tolerated dose below the baseline dose, but not less than 7.5 mg/week for the duration of the study. MTX should be given orally or parenterally.

Switching between routes of administration of MTX or dose adjustment for any reason other than toxicity is not permitted during the SBTP. Adjustments in MTX dosing and route of administration are allowed at the investigator's discretion in the OLTP.

All participants must receive folic acid, folinic acid, or leucovorin according to the manufacturer's recommendations.

7.2 Method of Treatment Assignment

All participants will be centrally randomized using an IRT. Before the study is initiated, each user will receive log-in information and directions on how to access the IRT. Each participant will be assigned a unique participant number after signing the ICF. Participant numbers will be used on all participants' study information. Participant numbers will not be reassigned. The investigator or designee will register the participant for enrollment by following the enrollment procedures established by the Sponsor.

The following information is required for enrollment:

- Date that informed consent was obtained
- Year of birth
- Gender at birth

Once enrolled in IRT, enrolled participants who have met all eligibility criteria will be ready to be randomized through the IRT. The following information is required for participant randomization:

- Participant number
- Year of birth
- Gender at birth (female or male)
- SE status (positive or negative)

The exact procedures for using the IRT will be detailed in the IRT manual.

Study treatment will be dispensed at the study visits as listed in [Section 2](#) (Schedule of Activities). Sufficient drug will be dispensed at each visit to cover treatment until the next scheduled visit. These will be in intervals of 4, 8, or 12 weeks according to the visit schedule.

